### **7.1 Baseline Visit**

The baseline visit will occur  $\leq$  28 days after written informed consent is obtained and include the following:

- Demographics and medical history, including prior and current medical conditions or illness, and allergies to medications.
- Date of diagnosis with CRPC, with confirming serum PSA values and associated hormonal therapy.
- Confirmation of no current or prior treatment with investigational therapy for M0 CRPC, Taxotere (docetaxel), Provenge® (sipuleucel-T), Zytiga (abiraterone acetate), Xtandi (enzalutamide), Jevtana (cabazitaxel), or Xofigo (radium Ra 223 dichloride).
- Prostate cancer imaging study history.
- Confirmation that no imaging study to determine the presence of bone or soft tissue metastases was performed  $\leq$  3 months prior to the date written informed consent was obtained.
- ECOG performance status.
- Height and weight.
- ACE-27.
- Gleason score.
- Serum PSA history.
- Current opioid analgesic use (yes/no).
- Concomitant medications (prescription medications only).
- Pain status (with BPI).
- Previous and ongoing prostate cancer interventions. Prostate cancer interventions include but are not limited to radiation, chemotherapy, hormonal therapy, investigational cancer therapies, all other systemic therapies (including steroids), and surgery for prostate cancer. Record indication(s) for choice of therapy, starting dose, timing (start and stop dates), and rationale for starting and stopping therapy (e.g., PSA progression) on the eCRF.
- Bone and soft tissue imaging studies for detection of metastatic prostate cancer.
- Blood sample for clinical laboratory tests at local laboratory, as indicated in the Schedule of Assessments ([Table 1](#)).
- Blood sample for biomarker analysis, providing the patient has consented to AOR.

## 7.2 Registration

Registration occurs after the inclusion and exclusion criteria have been confirmed.

### 7.3 Scheduled 6-Month M0 Phase Study Visit

For patients in the M0 Phase, scheduled visits will occur every 6 months ( $\pm$  1 month), starting 6 months from the date of the patient's registration, and will continue until 3 years after the last patient is registered. All data that have become available since the previous visit regarding the parameters listed below will be collected. Imaging studies are optional and will be determined by investigator assessment of need. Any imaging study that occurs within 1 month of a 6-month M0 Phase study visit will be considered part of that 6-month M0 Phase study visit, and no repeat assessments will be required.

The following will occur at each scheduled 6-month M0 Phase study visit:

- ECOG performance status.
- Current opioid analgesic use (yes/no).
- Pain status (with BPI).
- Prostate cancer interventions as described in Section [7.6.13](#).
- Survival status. The terms "alive" with the date of confirmation, "deceased", or "unconfirmed" are collected. For those patients recorded as "deceased", an additional eCRF page entitled "Date and Cause of Death" will become available. On this page, "Date of death" and "Cause of Death (check all that apply): Disease progression, Cardiac event, New primary cancer, Cerebrovascular event, and other (specify)", are listed as choices.
- Bone and soft tissue imaging studies for detection of metastatic prostate cancer (optional).
- Blood sample for clinical laboratory tests at local laboratory, as indicated in the Schedule of Assessments ([Table 1](#)).
- Serious adverse events in patients who receive at least 1 partial ( $> 0$  mL) infusion of Provenge that occur  $\leq$  30 days after the last infusion, regardless of relationship to Provenge;
- Blood sample for biomarker analysis, providing the patient has consented to AOR. This sample is collected within  $\pm$  1 month of an imaging study if it occurs during the  $\pm$  1 month visit window.

### 7.4 M0 Phase Imaging Visits

This visit occurs if the investigator determines that imaging study(ies) is/are needed to assess development of metastatic disease (M1 CRPC) and the imaging occurs  $>$  1 month after baseline or more than 1 month before or after a 6-month M0 Phase study visit. The following will occur during the visit:

- ECOG performance status.
- Current opioid analgesic use (yes/no).

- Pain status (with BPI).
- Prostate cancer interventions as described in Section [7.6.13](#)
- Survival status as described in Section [7.6.14](#).
- Bone and soft tissue imaging studies for detection of metastatic prostate cancer.
- Blood sample for clinical laboratory tests at local laboratory, as indicated in the Schedule of Assessments ([Table 1](#)).
- Serious adverse events in patients who receive at least 1 partial ( $> 0$  mL) infusion of Provenge that occur  $\leq$  30 days after the last infusion, regardless of relationship to Provenge.
- Blood sample for biomarker analysis (within  $\pm 1$  month of imaging), providing the patient has consented to AOR.

Any imaging study that occurs within 1 month of a 6-month M0 Phase study visit will be considered part of that 6-month M0 Phase study visit, and no repeat assessments will be required.

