### **8.3.2 Secondary Endpoints**

The proportion of patients who receive a diagnosis of M1 CRPC at the time of the baseline imaging study will be categorized as metastatic due to soft tissue (nodal and/or visceral) metastases, bone metastases, or both. The percentage of patients in each category will be computed based on the primary analysis population.

Logistic regression analyses, similar to the analyses described for the primary endpoint, will be used to identify characteristics predictive of an imaging study positive for M1 in the M0 population. Analyses will be performed using baseline information only as predictor variables with the outcome variable as a positive imaging study (yes/no) at any post-baseline time point. In addition, an analysis will be performed on the M0 population using all imaging studies collected in the study as the outcome variable (positive=yes/negative=no) with predictor variables associated with each imaging study. Appropriate methods accounting for the correlation of multiple studies for a patient, such as generalized estimating equations, will be used for this analysis. Cox regression analyses incorporating information on the time to occurrence of a positive imaging study will be performed to supplement these analyses.

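### In the per-scan and post-baseline biomarker analyses, predictors may be measured up to a month after the scan they predict, or be missing because that scan was positive

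*Combined protocol and SAP*

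**What the plan says.** Sections 7.3 and 7.4 and note h of Table 1 set the pairing rule. "Any imaging study that occurs within 1 month of a 6-month M0 Phase study visit will be considered part of that" visit (Section 7.4), in either direction. Section 7.3 adds that such a scan is "considered part of that 6-month M0 Phase study visit, and no repeat assessments will be required". The values attached to that scan are then the visit's ECOG status, BPI, opioid use, laboratory tests and PSA.

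At a separate imaging visit these assessments take place at the visit itself. Only the biomarker sample has a window there, 1 month either side of the scan: "Blood sample for biomarker analysis (within" ± 1 "month of imaging), providing the patient has consented to AOR". Sections 7.3 and 7.6.17 give a similar window.

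Section 8.3.2 has two logistic analyses of later scans. For one, "Analyses will be performed using baseline information only as predictor variables". The other is run "using all imaging studies collected in the study as the outcome variable (positive=yes/negative=no) with predictor variables associated with each imaging study", with generalized estimating equations or a similar method. Cox regression supplements both. Section 8.3.3 carries the approach over to biomarkers and adds time-varying ECOG and laboratory covariates for metastasis-free survival.

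Other passages bear on what is collected after a positive scan:
- Section 4.0 (M1 Phase) moves a man with a positive scan to the M1 schedule from the next 6-month visit. Under Table 1 that schedule has no BPI and no biomarker sample.
- Section 7.6.16 states that no study blood is drawn for laboratory tests or PSA in M1 Phase; available results are recorded.
- Section 7.6.17 ends biomarker sampling at M1 diagnosis.
- Section 7.5 and note d of Table 1 provide for a 6-month M0 visit that itself includes a positive scan.

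The SAP was not finalized, so it supplies no timing rule.

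**The concern.** Section 1.2 says the data should help guide when to image. A predictor serves that purpose only if its value is known before the scan. Under the pairing rule it may be recorded after the patient has been told the result, or after treatment has been started because of it. Pain reports and opioid use could change through knowledge or treatment; PSA and blood biomarkers could change mainly through treatment.

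Only men with a positive scan learn that they have M1 disease. The error therefore falls on one outcome group and does not average out. A variable with no predictive value could enter the model, and a useful one could be weakened. If the values are missing for the same men instead, the analysis loses predictor data according to outcome, which is also a bias.

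**Working it through.** **The two readings side by side.** Take a man scanned two weeks before his 6-month M0 visit, with a positive result.
- *Merging rule (7.3, 7.4, 7.5, Table 1 notes d and h).* The scan belongs to that M0 visit. His BPI, ECOG, opioid use, laboratory tests and PSA from the visit are paired with it, two weeks after the scan.
- *Strict phase rule (4.0, 7.6.16, 7.6.17).* He is in M1 Phase, and the visit follows the M1 schedule. BPI, study blood draw and biomarker sample are not taken. ECOG and opioid use are still collected, but after the scan; whether they may be paired with it is not stated.

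A man with a negative scan on the same date has all these values under both readings.

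**The plan's own figure (Section 8.1).** This concerns the baseline primary endpoint and serves here only as a yardstick.
- Odds ratio: (0.3495/0.6505) / (0.2905/0.7095) = 1.312.
- Power with 1000 per level: pooled rate 0.32; null SE = √(0.32 × 0.68 × 2/1000) = 0.02086; alternative SE = 0.02082; z = (0.059 − 1.96 × 0.02086)/0.02082 = 0.87; power 0.808. The stated 80% is reproduced.

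**Illustration of size.** The documents give no contamination rate, predictor prevalence or number of post-baseline scans. Assumptions:
- 1360 independent scans, one per M0 patient. The patient number follows from 2000 × (1 − 0.32), using the M1 share expected in Section 8.1.
- 20% to 32% of scans positive.
- A yes/no predictor with no true association and prevalence x of 10%, 20% or 30%.
- c = the share of men with a positive scan and a true value of no who are recorded as yes because assessment followed the result; 2%, 5% or 10%.

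Formulas: prevalence among positives x₊ = x + (1 − x)c; apparent OR = [x₊/(1 − x₊)] / [x/(1 − x)]; rejection rate from the pooled two-proportion test, 2-sided 5%.

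Worked case, x = 10%, c = 5%, 20% positive: x₊ = 0.10 + 0.90 × 0.05 = 0.145. OR = (0.145/0.855)/(0.10/0.90) = 1.53. There are 272 positive and 1088 negative scans; pooled prevalence 0.109; null SE 0.02113; alternative SE 0.02321; z = (0.045 − 1.96 × 0.02113)/0.02321 = 0.15; rejection rate 56%.

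| Prevalence | c | Apparent OR (true 1.00) | False-positive rate |
|---|---|---|---|
| 10% | 2% | 1.20 | 15–18% |
| 10% | 5% | 1.53 | 56–67% |
| 10% | 10% | 2.11 | 97–99% |
| 20% | 2% | 1.10 | 10–11% |
| 20% | 5% | 1.26 | 31–39% |
| 20% | 10% | 1.56 | 80–90% |
| 30% | 2% | 1.07 | 8% |
| 30% | 5% | 1.18 | 21–26% |
| 30% | 10% | 1.37 | 60–73% |

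A spurious odds ratio equal to the yardstick of 1.312 needs c of 3.0%, 5.9% or 8.6% at prevalence 10%, 20% or 30%. With predictors limited to values that precede the scan or its disclosure, c = 0, the odds ratio is 1.00 and the test keeps its 5%.

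**The case against.** The strongest reply is that men with positive scans leave the M0 schedule, so contaminated BPI, blood and biomarker values are never collected. That is a fair reading of Sections 4.0, 7.6.16 and 7.6.17, and it means the stop on biomarker sampling is not the only limit in the plan. But it conflicts with the merging rule and with Section 7.5 and note d of Table 1. Where it applies, it replaces contaminated values by values missing for positives only.

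Second, the reach is limited. The window is two-sided, and a value taken before the scan does no harm. At separate imaging visits only the biomarker sample has a window. A reader might infer that the primary analysis is compromised as well. The documents do not support that: the 1-month rule governs M0 Phase visits, and the baseline-only analysis of later scans is likewise outside it. For baseline, one can say only that Section 7.1 sets no order among pain, bloods and imaging.

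Third, scan, disclosure, treatment and a changed PSA would all have to fit within a month, and no document figure shows how often that happens. This stands, and it is why no PSA effect is quantified here.

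Fourth, data since the previous visit and intervention start and stop dates are collected (Sections 7.3 and 7.6.13), so an analyst could identify some values taken after treatment began. That helps, but the plan does not require it, and treatment dates do not show when a patient learned his result.

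**Conclusion.** The point holds for the secondary per-scan analysis, for any Cox supplement with time-updated covariates taken from paired visits, and for the post-baseline biomarker analyses. As written, the plan either admits predictors measured after a positive result is known or acted on, or leaves them missing for men with positive scans. Both bias the analysis according to outcome.

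The size cannot be derived from the documents. The range of apparent odds ratios, about 1.07 to 2.11, and of false-positive rates, about 8% to 99%, rests wholly on the assumed prevalence, switching share, scan number and positive rate. It shows that modest contamination is enough to matter; it does not estimate what would occur. A reader might take it as evidence that pain or opioid findings would be spurious. It is not.

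**What to change.** **Sections 8.3.2 and 8.3.3, post-baseline scans.** Admit as predictors only values dated on or before the scan, or before its result is disclosed. Otherwise use the last earlier value. Add a sensitivity analysis of the age of the value used.

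**Sections 7.3 and 7.4, and as a precaution 7.1.** Complete the BPI, ECOG, opioid question and blood draws before the scan result is given to the patient. Record the dates of scan, result and each assessment. This concerns the order of data collection only.

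**Reconcile** Sections 4.0 (and the matching Synopsis text), 7.6.16 and 7.6.17 with Sections 7.3, 7.4 and 7.5 and Table 1 notes d and h, so that it is clear which assessments a man has when a positive scan falls shortly before a 6-month visit.

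Do not apply the last-earlier-value rule to baseline BPI, ECOG or opioid use. They are first collected at baseline, so no earlier study value exists.

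**Cost.** A dating rule, a site instruction and a few date fields, with no extra patients, visits or tests; the sample size is unchanged. Some post-baseline scans would use values up to about 6 months old, since the previous scheduled visit may be the last source.

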## 7.5 M1 Phase Data Collection

The M1 Phase will be observational. For patients in M1 Phase, data will be collected every 6 months ( $\pm 1$  month) until 5 years after the last patient is registered.

At each 6-month time point during M1 Phase, all data that have become available since the previous time point regarding the parameters listed below will be collected. For patients who enter M1 Phase because of an M0 Phase study visit that includes an imaging study positive for M1, all such data that have become available since the last scheduled 6-month M0 Phase study visit will be collected.

The data to be collected during M1 Phase include:

- ECOG performance status.
- New sites of metastases.
- ACE-27 assessment (for those patients who enter M1 Phase because of an M0 Phase study visit that includes an imaging study positive for M1, an ACE-27 is required to be completed within 6 months after the patient's last M0 phase study visit).
- Current opioid analgesic use (yes/no).
- Prostate cancer interventions as described in Section [7.6.13](#).
- Survival status as described in Section [7.6.14](#).

- Clinical laboratory results (alkaline phosphatase, hemoglobin, LDH, serum albumin, and serum PSA).
- Serious adverse events in patients who receive at least 1 partial ( $> 0$  mL) infusion of Provenge that occur  $\leq 30$  days after the last infusion, regardless of relationship to Provenge.

Data collection during M1 Phase may occur by clinic visits, reviews of the patient's medical record, or telephone calls, with the call documented in the patient's medical record. Clinic visits or telephone calls may occur by the following methods:

- Patient visit at the study site.
- Telephone call from the study site to the patient's physician.
- Telephone call between the study site and the patient.

**Table 1: Schedule of Assessments—M0/M1 Phases**

Event	Baseline	M0 Phase		M1 Phase
Timing	≤ 28 days after informed consent obtained	From date of registration until 3 years after last patient is registered		From date of registration until 5 years after last patient is registered
		6-month M0 Phase study visit (± 1 month)	M0 Phase imaging visit as needed (> 1 month after previous study visit)	Data collection every 6 months (± 1 month)
Clinical evaluations				
Demographics and medical history	X			
Date of diagnosis with CRPC, with confirming serum PSA values and associated hormonal therapy	X			
Prostate cancer imaging study history	X ab			
ECOG performance status	X	X	X	X
New sites of metastases		X	X	X
Height and weight	X			
Registration	X c			
Prognostic factors and other evaluations				
ACE-27	X			X d
Gleason score	X			
Serum PSA history e	X			
Current opioid analgesic use (yes/no)	X	X	X	X
Concomitant medications	X			
Pain status with Brief Pain Inventory	X	X	X	
Prostate cancer interventions f	X	X	X	X
Survival status		X	X	X
Imaging studies (bone and soft tissue)g	X	Optional h	X	
Clinical laboratory tests				
Alkaline phosphatase, hemoglobin, LDH, serum albumin	X	X	X	X i
Serum PSA	X	X	X	X i
Testosterone	X			
Safety Eventsj		X	X	X
AOR	X	X	X	

Abbreviations: ACE-27=Adult Comorbidity Evaluation-27; AOR=additional optional research (for biomarkers); CRPC=castration-resistant prostate cancer; ECOG=Eastern Cooperative Oncology Group; eCRF=electronic case report form; LDH=lactate dehydrogenase; M0=no distant metastases; M1=distant metastases; PSA=prostate-specific antigen; SAE=serious adverse event.

- a Patients who have undergone an imaging study to determine the presence of M1 (bone and/or soft tissue)  $\leq 3$  months prior to signing the informed consent form are not eligible.
- b Record prostate cancer imaging studies completed from the time of biochemical recurrence after primary therapy until the baseline visit.
- c Registration occurs after the inclusion and exclusion criteria have been confirmed
- d For those patients who enter M1 Phase because of a positive imaging study at a 6-month M0 Phase study visit or an M0 Phase imaging visit, clinic staff will complete the ACE-27 within 6 months after the patient's most recent M0 Phase study visit and not at other time points.
- e All serum PSA values from the date of diagnosis with CRPC until the date of written informed consent, where available, will be recorded on the eCRF.
- f Prostate cancer interventions include but are not limited to radiation, chemotherapy, hormonal therapy, investigational cancer therapies, all other systemic therapies (including steroids), and surgery for prostate cancer. Record indication(s) for choice of therapy, starting dose, timing (start and stop dates), and rationale for starting and stopping therapy on the eCRF.
- g The number and sites of bone, regional or distant nodal or visceral metastases, if present, will be recorded on the eCRF. Choice of imaging modality depends on study site's standard of care; the same modality should be used for all images for a given patient until diagnosis of M1 CRPC. However, if modality is changed and diagnosis of M1 CRPC occurs during first use of a new imaging modality, an additional imaging study with the previous modality will be performed within 1 month of the positive imaging study; this additional imaging study will be reimbursed by the sponsor. However, if the change is from a higher to a lower sensitivity modality, the higher sensitivity modality will not be repeated.
- h Frequency of imaging studies will be at investigator's assessment of need. Imaging studies performed within 1 month of a 6-month M0 Phase study visit will be considered part of that visit.
- i For patients in M1 Phase, clinical laboratory results, including serum PSA data, that have become available since the previous time point for data collection will be recorded on the eCRF.
- j For patients who receive at least 1 partial ( $>0$  mL) infusion of Provenge, record SAEs that occur  $\leq 30$  days after the last infusion, regardless of relationship to Provenge.

## **7.6 Procedures and Assessments**

### **7.6.1 Demographics and Medical History**

The following demographic data will be recorded on the eCRF for all patients: date of birth, ethnicity, and race.

The following medical history information will be recorded on the eCRF at the baseline visit: historic and current medical conditions or illness, allergies to medications, and prior prostate cancer interventions, including therapies and surgical procedures.

### **7.6.2 Date of Diagnosis with CRPC**

The date of diagnosis with CRPC will be confirmed at the baseline visit. A sequence of 2 rising serum PSA values (compared to a nadir value) measured at least 7 days apart where the second value is  $\geq 2$  ng/mL ([Scher 2008](#)), in the setting of surgical or continuous medical castration (defined as testosterone  $\leq 50$  ng/dL with either an LHRH agonist or antagonist as monotherapy) is required. Patients who subsequently receive combination and/or secondary hormonal treatments (e.g., CAB) that reduce or control their serum PSA elevation are considered to have CRPC and are eligible for the study.

The date of diagnosis with CRPC is defined as the date of the first serum PSA value above nadir in the sequence of serum PSA values used to confirm the presence of CRPC. The date of diagnosis with CRPC will be recorded on the eCRF.

### **7.6.3 Prostate Cancer Imaging Study History**

At the baseline visit, all previous imaging studies for prostate cancer (type and date) that were completed from the time of biochemical recurrence after primary curative therapy until the baseline visit will be recorded on the eCRF. For patients who have not received primary curative therapy, all imaging studies completed from the time of diagnosis until the baseline visit will be recorded on the eCRF.

Biochemical recurrence is defined as a rising serum PSA after primary curative therapy as follows:

- If primary therapy was RP (with or without external beam radiation therapy), rising serum PSA is defined as 2 consecutive rising values above 0.2 ng/mL, each taken  $\geq 3$  weeks apart, and the last value is  $\geq 0.5$  ng/mL.
- If primary therapy was external beam radiation, rising serum PSA is defined per the Phoenix definition ([Roach 2006](#)), i.e., as 2 consecutive rising values, each taken  $\geq 3$  weeks apart and above the serum PSA nadir plus 2.0 ng/mL.

